5. INTERIM ANALYSES

A purely Administrative Interim analysis (IA) will be conducted internally at AZ with no consequences for the trial. Therefore, the details of the IA are outside the scope of the SAP, as no interim outputs will be provided in the CSR.

5.1 Sensitivity analysis

An analysis will be conducted on the primary outcome variable, loss of asthma control, using the same log rank test as for the primary analysis, but making the assumption that all patients who withdraw from the study without recorded loss of control are classed as loss of control (instead of being censored), in order to test the sensitivity of the results to the use of censoring/lack of information regarding loss of control in patients who withdraw.

Summary statistics will be produced for the reliever medication for each treatment group over time for the weekly average and the change from baseline in weekly average by 1) imputing missing values to zero and 2) imputing using last observation carried forward (LOCF) method.

Summary statistics will be produced for Asthma Symptom scores (weekly total: mean total daily score, number of asthma symptom free days and proportion of asthma symptom free days endpoints) for each treatment group over time for the weekly average by 1) imputing missing values to zero and 2) imputing using last observation carried forward (LOCF) method.

For LOCF, the missing values will be populated until the patient has their next non-missing value or until the patient either completes the study or withdraws from the study. For both imputation methods, the individual missing values should be imputed (not daily sums or weekly averages).

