3.5 Methods for assigning treatment groups

The randomization scheme for this study will be generated by the biostatistics group at AstraZeneca or designee. This will be done using AZRand system. Randomization will be performed through a centralized interactive voice and web response system (IxRS). Patients will be block randomized 1:1 to either placebo or AZD1419, with no stratification.

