1.3 Number of patients

This trial has about 90% power to yield a statistically significant ($\alpha = 0.05$, 2-sided) difference between the pooled active and placebo groups in time to loss of asthma control given that the cumulative number of controlled patients at week 52 is 20% and 60% for control versus active respectively. Assuming a drop-out of about 10-15%, this will require about 70 patients in total (32 events).

Approximately 135 patients have been enrolled to achieve 81 randomised patients.

Figure 1
Study flow
chart

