1. Date of the first increase in ACQ-5 of 1.5 or more
2. Date of the first of two consecutive days with a reduction of 30% or more in PEF
3. Date of the first of two consecutive days with six additional SABA inhalations relative to baseline
4. Date of the earliest use of systemic corticosteroids to treat an asthma exacerbation

Time to loss of asthma control will be censored at 52 weeks for patients who do not experience loss of asthma control during the 52-week study period or at the time point after which an loss of asthma control experience could not be assessed (for lost-to-follow-up patients). For patients who withdraw from the study without reporting loss of asthma control, time will be censored at the date of withdrawal, if known, else at the patient's last clinical visit plus one day.

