4.2.4 Analysis of the primary variable

Under a proportional hazard assumption, we can define the hazard ratio as $\theta = H_A(t)/H_B(t)$ for all $t \leq \tau$, τ is the largest observation time. A represents the active treatment arm (AZD1419), B represents placebo and $H(t)$ is the hazard function. To compare the effect of active treatment AZD1419 to placebo group, a log-rank (Mantel-Cox χ^2) test will be carried out using the SAS[®] procedure PROC LIFETEST, where the null hypotheses will be:

$$H_0: \theta = 1$$

$$H_1: \theta < 1$$

The null hypothesis (H_0) is that during the 52-week double-blind treatment period, the time to loss of asthma control in the AZD1419 arm is equal to the corresponding time to loss of asthma control in the placebo arm. The alternative hypothesis (H_1) is that the time to loss of asthma control in the active arm (AZD1419) is longer than in the placebo arm.

Time to loss of asthma control will be displayed graphically using a Kaplan-Meier plot (time axis, will be time from randomisation).

A Cox proportional hazard model will be fitted to the data to compare the treatments using the SAS[®] procedure PROC PHREG. Results of the analysis will be summarized as hazard ratio, 2-sided 95% confidence interval and p-value comparing AZD1419 with placebo. The hypothesis test will be 1-sided, with $\alpha=0.05$. The covariates for inclusion in the statistical model are described in Section 4.2.1.

For patients who withdraw from the study without reporting loss of asthma control, time will be censored at the date of withdrawal, if known, else at the patient's last clinical visit plus one day.

The assumptions underlying the statistical model will be explored. If the proportional hazards assumption does not hold then alternative methods will be explored which may include the following: 1) Extend the model to include exposure-time interaction term or 2) if the variable for which there is evidence of non-proportional hazards is a confounder, rather than the main exposure of interest then regression may be stratified.

Sensitivity analysis will be performed on the primary variable, see Section 5.1.

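### The only sensitivity analysis of the primary endpoint is a real check when withdrawals are equal or in excess on AZD1419, but gives almost none when they are clearly in excess on placebo

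*SAP*

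**What the plan says.** The primary test is a one-sided log-rank test at 0.05 (SAP 4.2.4). Patients without loss of control are censored at the end of follow-up: "Time to loss of asthma control will be censored at 52 weeks" (SAP 3.2). Those who withdraw earlier without a recorded event are censored at withdrawal, in both arms.

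For sensitivity analysis of the primary variable, SAP 4.2.4 points only to Section 5.1. That section repeats protocol 8.4.7: the same log-rank test, "making the assumption that all patients who withdraw from the study without recorded loss of control are classed as loss of control". The stated aim is to see how far the result depends on censoring and on missing information after withdrawal. The other items in 5.1 are summary statistics for reliever use and symptom scores. The Cox model in 4.2.4 keeps the primary censoring. No one-directional, reference-based or tipping-point analysis of the primary endpoint is planned.

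On drop-out, SAP 1.3 gives only an overall figure: "Assuming a drop-out of about 10-15%, this will require about 70 patients in total (32 events". Neither document gives rates by arm.

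**The concern.** The primary claim is one-directional: AZD1419 delays loss of control. A check on that claim should be able to weaken it whichever arm loses more patients. Turning an AZD1419 withdrawal into an event works against the drug, and turning a placebo withdrawal into an event works for it. The planned analysis does both, so its net push depends on which arm loses more patients.

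If placebo loses clearly more, the check is easier to pass than the primary test. A chance-positive primary result would then almost always be repeated, and that agreement could be read as robustness to drop-out when it shows nothing of the kind.

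**Working it through.** **Inputs.**
- Randomised: 81 (SAP 1.3: "Approximately 135 patients have been enrolled to achieve 81 randomised patients"), allocated 1:1 (protocol 3.5), so 40 placebo and 41 AZD1419.
- Test: one-sided log-rank, 0.05, critical value 1.645. Follow-up is 52 weeks, taken as one time unit.
- Planned effect: "cumulative number of controlled patients at week 52 is 20% and 60% for control versus active respectively" (SAP 1.3).
- Assumed, not in the documents: exponential times, withdrawal independent of outcome unless stated, the arm split, and 30% controlled in both arms for the no-effect case.

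**The plan's own figure.** HR = ln 0.6 / ln 0.2 = 0.317. Schoenfeld events, two-sided 0.05, 90% power: 4 × (1.960 + 1.282)² / (ln 0.317)² = 32. This matches the SAP. The sizing is two-sided and the test one-sided, which does not affect this point.

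**Mechanism.** Let λ be the hazard of losing control, equal in both arms when the drug does nothing, and ω the withdrawal hazard in each arm. The primary HR is 1. The planned sensitivity analysis estimates (λ + ω_active) / (λ + ω_placebo), which is below 1 whenever placebo withdraws faster.

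**Size.** λ = −ln 0.3 = 1.204. If a proportion w would withdraw by Week 52 in the absence of loss of control, ω = −ln(1 − w). Expected events are d = 40 × [1 − 0.3(1 − w_placebo)] + 41 × [1 − 0.3(1 − w_active)]. The test statistic shifts by −ln(HR) × √d / 2, and the rejection rate is P(Z > 1.645 − shift).

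| Withdrawals, placebo v AZD1419 | HR | d | Shift | Rejection |
|---|---|---|---|---|
| 15% v 10% | 1.309/1.366 = 0.96 | 59.7 | 0.17 | 7% |
| 20% v 5% | 1.255/1.427 = 0.88 | 59.7 | 0.50 | 12.5% |
| 25% v 5% | 1.255/1.492 = 0.84 | 60.3 | 0.67 | 16.5% |
| 5% v 20% | 1.427/1.255 = 1.14 | 59.8 | −0.50 | 1.6% |

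Simulation (4,000 trials per scenario) gives about 7%, 12–13% and 16–19% for the first three rows. The primary test stays near 5%.

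**How often does it overturn a chance-positive primary result?**
- 20% v 5% and 25% v 5%: it confirms about 98–100% (97% in the lowest single run).
- Equal withdrawals, 12.5% per arm: it rejects in 4.5% and confirms 70% (simulated with 20% controlled).
- 5% v 20%: it confirms only 15–34%.
- If 20–30% of AZD1419 patients who would lose control withdraw at onset instead, the primary test rejects in 22–37% of no-effect trials and the planned analysis brings this back to 5% (20% controlled).

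**Dependence on how withdrawal is counted.** The table treats w as the chance of withdrawing if control were never lost. Some of those patients lose control first, so fewer withdrawals are observed. If 20% v 5% means observed withdrawals before any event (12.5% overall, within the SAP's 10–15%), the effect is larger. With 20% controlled, λ = 1.609, and solving ω/(λ+ω) × [1 − e^−(λ+ω)] = w gives ω = 0.476 and 0.105. Then HR = 1.714/2.085 = 0.82, and simulation rejects in 21% (23% with 40% controlled). The table is therefore the milder reading.

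**The additions.** Counting AZD1419 withdrawals as events and censoring placebo withdrawals rejects in 1–4% of no-effect trials at 20% v 5% and 25% v 5%. With no AZD1419 withdrawals (25% v 0%) it is identical to the primary test (5.8% for both in simulation). The extreme case, with placebo withdrawals also event-free to Week 52, rejects in 0.1–0.3% (20% controlled, observed withdrawals). Under the planned effect with 12.5% withdrawal per arm, power is about 97–98% for the current analysis and 89–95% for the one-directional version. The extreme case has 76% power when the 12.5% is observed withdrawals.

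**The case against.** A reader might infer that the planned analysis can never show whether a positive result depends on drop-out. The documents do not support that. It holds its size when withdrawals are equal, is severe when AZD1419 loses more patients, and corrects the case where AZD1419 patients leave as they lose control.

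Nor do the documents say that placebo will lose more patients. Worsening patients are meant to be captured as events through daily monitoring, alerts and a composite definition (protocol 1.3 and 4.3). One exit without an event that could differ by arm, not tolerating the lowest dose level (protocol 4.2.2), could load on AZD1419. An excess on placebo remains possible, since controllers are withdrawn and protocol 1.3 recognises the risk of worsening. The split is unknown when the plan is fixed.

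Other material partly offsets the gap. The proportion in SAP 3.3.1 divides events by all patients in the group, so a withdrawal counts as no event and excess placebo withdrawals work against AZD1419. A simple one-sided two-proportion test on that definition rejects in 2.0% at 20% v 5% and 1.5% at 25% v 5%. SAP 4.2.1 reports study discontinuation by arm with reasons, and Kaplan-Meier plots of withdrawal. These would reveal an imbalance, but the first is not a time-to-event check and the second does not show what an imbalance does to the primary result.

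A reader might also infer that the trial's type I error is inflated. It is not: in these scenarios the primary test stays near 5%, and the SAP makes no decision depend on the sensitivity analysis.

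**Conclusion.** The point holds in one direction. The single planned sensitivity analysis is informative when withdrawals are equal or in excess on AZD1419, and gives almost no check on a positive result when they are clearly in excess on placebo. The size depends on the assumed split: slight at 15% v 10%, but more than twice the nominal 5% at 20% v 5% and about three to four times at 25% v 5%. The figures rest on exponential event times, withdrawal unrelated to outcome, 81 patients and 30% controlled in both arms. Counting observed rather than potential withdrawals makes them larger. What is at stake is the evidence of robustness to drop-out, not the validity of the primary test.

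**What to change.** Keep the current analysis in SAP 5.1, labelled as the symmetric case. Add, before unblinding (protocol Section 8 allows SAP amendments until then):

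1. The same log-rank test with AZD1419 withdrawals as events at withdrawal and placebo withdrawals censored as in the primary analysis.
2. A tipping-point analysis that varies the outcome of withdrawals in both arms, up to placebo withdrawals staying event-free to Week 52. This is needed because version (1) adds nothing if no AZD1419 patient withdraws.

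Describe the primary result as robust to drop-out only in light of all of these together. No single one should act as the gate.

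The cost is one more run of an existing procedure for (1), some programming for (2), and no new data. The downside is that a less favourable figure is reported, although a true effect of the planned size would usually survive version (1).

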6. CHANGES OF ANALYSIS FROM PROTOCOL

Updated detail to categorization of AE data.

Additional Cox proportional hazards model added for loss of asthma control for the primary endpoint

Additional Cox proportional hazards model added for time to first moderate or severe exacerbation as a secondary endpoint.

Additional summary statistics for asthma daily diary score

Additional logistic regression analysis added to the analysis of reliever bronchodilator

Updated detail to the analysis of CompEx, using a Cox hazard model, and a log binomial regression model as well as Kaplan Meier plots.

Updated statistical models for ACQ-5, Asthma Daily Diary score, PEF and FeNO to add a treatment*week interaction term.

Additional summary statistics for PEF.

Choice of covariates described for Blinded Deliverable review analyses and final analysis.

Summary statistics for time to loss of asthma control added.

Sensitivity summary statistics proposed for Reliever Medication and Asthma Symptom scores.

Changed a secondary endpoint definition from ‘proportion of patients who experience ≥ 1 moderate or severe exacerbation during the 52-weeks of treatment’ to ‘proportion of patients who experience 1 moderate or severe exacerbation during the 52-weeks of treatment’.

Clarified the time to event analysis for ‘moderate or severe exacerbation’.

Clarified the FAS definition to remove ambiguity. Patients that ‘did not take IP’ will not be in the FAS.

8. APPENDIX

8.1 Appendix A Analysis windows

Table 5 Analysis windows for weekly summaries

| Week | Adjusted windows for weekly measures using morning or daily assessments | Adjusted windows for weekly measures using evening assessments |
|-------------|--|---|
| 1 | 2-8 | 1-7 |
| 2 | 9-15 | 8-14 |
| 3 | 16-22 | 15-21 |
| 4 | 23-29 | 22-28 |
| 5 | 30-36 | 29-35 |
| 6 | 37-43 | 36-42 |
| 7 | 44-50 | 43-49 |
| 8 | 51-57 | 50-56 |
| 9 | 58-64 | 57-63 |
| 10 | 65-71 | 64-70 |
| 11 | 72-78 | 71-77 |
| 12 | 79-85 | 78-84 |
| 13 | 86-92 | 85-91 |
| 14 | 93-99 | 92-98 |
| 15 | 100-106 | 99-105 |
| 16 | 107-113 | 106-112 |
| 17 | 114-120 | 113-119 |
| 18 | 121-127 | 120-126 |
| 19 | 128-134 | 127-133 |
| 20 | 135-141 | 134-140 |
| 21 | 142-148 | 141-147 |
| 22 | 149-155 | 148-154 |
| 23 | 156-162 | 155-161 |

| Week | Adjusted windows for weekly measures using morning or daily assessments | Adjusted windows for weekly measures using evening assessments |
|-------------|--|---|
| 24 | 163-169 | 162-168 |
| 25 | 170-176 | 169-175 |
| 26 | 177-183 | 176-182 |
| 27 | 184-190 | 183-189 |
| 28 | 191-197 | 190-196 |
| 29 | 198-204 | 197-203 |
| 30 | 205-211 | 204-210 |
| 31 | 212-218 | 211-217 |
| 32 | 219-225 | 218-224 |
| 33 | 226-232 | 225-231 |
| 34 | 233-239 | 232-238 |
| 35 | 240-246 | 239-245 |
| 36 | 247-253 | 246-252 |
| 37 | 254-260 | 253-259 |
| 38 | 261-267 | 260-266 |
| 39 | 268-274 | 267-273 |
| 40 | 275-281 | 274-280 |
| 41 | 282-288 | 281-287 |
| 42 | 289-295 | 288-294 |
| 43 | 296-302 | 295-301 |
| 44 | 303-309 | 302-308 |
| 45 | 310-316 | 309-315 |
| 46 | 317-323 | 316-322 |
| 47 | 324-330 | 323-329 |
| 48 | 331-337 | 330-336 |
| 49 | 338-344 | 337-343 |
| 50 | 345-351 | 344-350 |
| 51 | 352-358 | 351-357 |
| 52 | 359-365 | 358-364 |

Table 6 **Analysis windows for scheduled visits**

| Visit | Target Day | Adjusted windows for scheduled visits |
|--------------------|-------------------|--|
| Visit 2 (Week 0)* | 1 | 1 - 4 |
| Visit 3 (Week 1) | 8 | 5-11 |
| Visit 4 (Week 2) | 15 | 12-18 |
| Visit 5 (Week 3) | 22 | 19-25 |
| Visit 6 (Week 4) | 29 | 26-32 |
| Visit 7 (Week 5) | 36 | 33-39 |
| Visit 8 (Week 6) | 43 | 40-46 |
| Visit 9 (Week 7) | 50 | 47-53 |
| Visit 10 (Week 8) | 57 | 54-60 |
| Visit 11 (Week 9) | 64 | 61-67 |
| Visit 12 (Week 10) | 71 | 68-74 |
| Visit 13 (Week 11) | 78 | 75-81 |
| Visit 14 (Week 12) | 85 | 82-88 |
| Visit 15 (Week 13) | 99 | 89-109 |
| Visit 16 (Week 16) | 113 | 110-127 |
| Visit 17 (Week 20) | 141 | 128-169 |
| Visit 18 (Week 28) | 197 | 170-225 |
| Visit 19 (Week 36) | 253 | 226-295 |
| Visit 20 (Week 48) | 337 | 296-351 |
| Visit 21 (Week 52) | 365 | 352-375 |

*Prior to first dose/randomisation, visits will be assigned to the Nominal visit. The visit windows will be applied thereafter.

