3.1.4 Visit windows

For the exacerbation-related analyses no windows will be applied.

Daily eDiary and ePRO data (PEF, ACQ-5, FeNO) will primarily be summarised and analysed as weekly averages e.g. over days 2 - 8, 9 - 15 and 16 - 22 etc, separately. The assessment period of visit windows will be defined in Appendix A, [Table 5](#).

Summaries and analyses of non-eDiary or non-ePRO data will be based on CRF visit designation, defined in Appendix A, [Table 6](#).

Any data collected at unscheduled visits will be listed, included within baseline data in shift plots, and will be included in the definition of maximum/minimum within-period value.

The Unscheduled visits will be included when applying the visit windows to ensure that all available data are used in the analysis. For weekly summaries, the mean of all non-missing observations within an assigned window is calculated. For visit data, if there are duplicate observations assigned to the same visit window, the following data handling conventions will be adopted:

1. If there are two or more observations within the same visit window, the non-missing observation closest to the scheduled visit will be used in the analysis.
2. If two observations are collected on the same day, the non-missing observation with the later collection time will be included in the analysis.

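### SAP Table 6 gives Visit 15 (Week 13) target Day 99 and window 89-109, where the pattern of the other rows gives Day 92 and 89-102

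*SAP*

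**What the plan says.** SAP Appendix A, Table 6 assigns clinic visits to analysis visits by study day. Each row gives a target day and a window.

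- The row at issue is the one labelled "Visit 15 (Week 13"; with its target and window it reads "Visit 15 (Week 13) | 99 | 89-109".
- The row above it, for the last dose, is "Visit 14 (Week 12) | 85 | 82-88".
- The row below it, for the next scheduled visit, is "Visit 16 (Week 16) | 113 | 110-127".
- Among the later, more widely spaced rows, the one for Week 20 is "Visit 17 (Week 20) | 141 | 128-169", while the one for Week 28 is "Visit 18 (Week 28) | 197 | 170-225".

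SAP 3.1.4 says how the windows are used. On unscheduled data it states: "The Unscheduled visits will be included when applying the visit windows". Where two or more observations share a window, "the non-missing observation closest to the scheduled visit will be used in the analysis". The same section also says that data from outside the diary and ePRO device are analysed by CRF visit designation, and it refers to Table 6 for the definition.

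SAP 3.3.10 schedules FVC and FEF25-75 at both Week 13 and Week 16. SAP 4.2.4.5 analyses FEV1 in a repeated-measures model with a treatment-by-visit term and reports results at each timepoint and overall.

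**The concern.** Visit 15 is labelled Week 13, but Day 99 is Week 14 under the SAP's own study-day convention. The upper limit of its window also reaches into days that lie closer to the Week 16 target. Because the plan keeps the observation closest to the scheduled visit, the target day is not just a label: it decides which value is analysed when two fall in the window.

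Week 13 is the first scheduled visit after the last dose at Week 12. A wrong target and boundary can put a later measurement in place of the Week 13 one, and can leave Week 16 without a value for the same patient. Both visits feed reported FEV1 contrasts.

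**Working it through.** **Inputs.** SAP 3.1.2 makes the day of randomisation (or first dose) Day 1, so a visit exactly w weeks later falls on Day 7w + 1. Targets and windows are the 20 rows of Table 6. The selection rule is in SAP 3.1.4.

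**1. Target days.** The formula 7w + 1 reproduces the printed targets for Weeks 0 to 12 (Days 1, 8, ..., 85) and for Weeks 16, 20, 28, 36, 48 and 52 (Days 113, 141, 197, 253, 337 and 365). That is 19 of 20 rows. For Week 13 it gives 7 x 13 + 1 = 92. The printed 99 is 7 x 14 + 1, which is Week 14. Table 5 agrees: for morning assessments, Week 13 is Days 86-92 and Week 14 is Days 93-99.

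**2. Boundaries.** Take the midpoint of adjacent 7w + 1 targets, round down for the upper limit, and start the next window one day later.

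| Visits | Midpoint | Pattern gives | Printed |
|---|---|---|---|
| 13/14 | (78 + 85)/2 = 81.5 | 81/82 | 81/82 |
| 14/15 | (85 + 92)/2 = 88.5 | 88/89 | 88/89 |
| 15/16 | (92 + 113)/2 = 102.5 | 102/103 | **109/110** |
| 16/17 | (113 + 141)/2 = 127 | 127/128 | 127/128 |
| 17/18 | (141 + 197)/2 = 169 | 169/170 | 169/170 |
| 18/19 | (197 + 253)/2 = 225 | 225/226 | 225/226 |
| 19/20 | (253 + 337)/2 = 295 | 295/296 | 295/296 |
| 20/21 | (337 + 365)/2 = 351 | 351/352 | 351/352 |

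The earlier weekly boundaries match as well, so 18 of the 19 boundaries are reproduced and only Visit 15/16 fails. The upper limit of Visit 21 (375) has no later visit to test it against.

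**3. Day 99 taken at face value.** The midpoints become (85 + 99)/2 = 92 and (99 + 113)/2 = 106, which gives a window of 93-106. The printed 89-109 matches at neither end. Its lower limit of 89 fits target 92, not 99. Days 107-109 lie closer to Week 16: Day 107 is 8 days from 99 and 6 from 113, and Day 109 is 10 and 4. The printed window is simply 99 +/- 10, and no other row with neighbours on both sides uses a 10-day margin.

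**4. Consequence under the selection rule.** A Week 13 value on Day 92 is |92 - 99| = 7 days from the printed target. Another value on Day e replaces it when |e - 99| < 7, that is, on Days 93-105. Day 106 ties at 7, and the SAP breaks ties only within the same day. A Week 16 visit replaces the Day 92 value only on Days 103-105, which is 113 - 105 = 8 to 113 - 103 = 10 days early. For example, with Visit 15 on Day 92 (distance 7) and Visit 16 on Day 105 (distance 6), the Day 105 value becomes Week 13, the Day 92 value is dropped, and Week 16 is empty unless another visit falls in its window.

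Visits on Days 103-109 (7 days) are assigned to Week 13, whereas the pattern would give them to Week 16. With target 92, a visit held on Day 92 has distance 0 and no other day can replace it.

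**The case against.** **The windows may not govern scheduled visits.** SAP 3.1.4 refers to CRF visit designation. If that prevails, a Visit 16 held on Day 105 stays Visit 16 and displaces nothing. This stands as a real ambiguity: the same section points to Table 6 and brings unscheduled visits into the windows, so the text supports either reading. The consequences in step 4 are therefore conditional.

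**The pattern is inferred.** The SAP writes out neither 7w + 1 nor a midpoint rule. The row is exactly 99 +/- 10, Visit 21 ends at 365 + 10, and the amendment history shows that the windows were revised, so a deliberate choice is possible. Against that, Visit 15 is called Week 13 in SAP 3.3.10, 3.4.5 and 3.4.6, and Days 107-109 are misplaced even if 99 was intended. The objection limits certainty about which correction is right. It does not make the row consistent.

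**It may hardly ever happen.** An early Week 16 visit has to be 8-10 days early to displace a Day 92 value. The permitted visit windows belong to Protocol Figure 1, which was not available for this review. This stands.

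**A stronger reading is tempting.** A reader might infer that loss-of-control visits, expected more often on placebo after controller withdrawal, replace planned Week 13 values and so bias the comparison. The documents do not establish this. Protocol 4.3 and 5.1.3.1 describe that visit as investigator evaluation, completion of the exacerbation module and biomarker sampling. They name neither spirometry nor DLco, and the unscheduled-visit column of Protocol Table 1 is not readable in the available text. Without a measurement of the same variable, nothing is displaced.

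A reader might also infer that early Week 16 visits displace DLco or physical-examination results. SAP 3.4.5 and 3.4.6 schedule neither at Week 16, and the physical-examination shift table in SAP 4.2.5.6 uses the last on-treatment observation.

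**Conclusion.** The Visit 15 row is inconsistent with the other rows of Table 6, with Table 5 and with its own target of 99. Against the pattern of the table, the target is 99 - 92 = 7 days late and 7 days (103-109) are assigned to the wrong visit.

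The effect on results depends on the day windows being applied as SAP 3.1.4 describes and on a second non-missing value of the same variable falling in the window. Within those limits it touches by-visit clinic data only: mainly the Week 13 and Week 16 FEV1 contrasts, and the FVC and FEF25-75 summaries, which are descriptive. DLco is affected only if it is measured at an unscheduled visit. The primary analysis uses event dates (SAP 3.2) and is not affected. Neither the frequency of displacement nor any difference between arms can be determined from the documents, so no claim of bias is made. This is a minor point that is easily corrected.

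**What to change.** In SAP Table 6, set Visit 15 to target Day 92 and window 89-102, and Visit 16 to window 103-127. If Day 99 was intended, give the reason and correct the week label and the boundaries; on the table's pattern these would be 82-92 for Visit 14, 93-106 for Visit 15 and 107-127 for Visit 16.

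Add a sentence to SAP 3.1.4 stating whether CRF visit designation or the day window governs scheduled visits. This is needed even after the cells are corrected, because a Visit 15 held off target could still lose to a nearer unscheduled value.

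The cost is three table cells, one sentence and the matching change to the visit-window programming, made before unblinding. Trial conduct does not change.
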